6.2 Dose Modifications

Dose modifications below are outlined for the Phase I portion of the trial. Further information on the Phase II dose modification will be determined after the MTD is established.

Treatment with romidepsin and ixazomib will use a cycle length of 28 days. Missed doses within a cycle will not be made up. For example, if drug is held on Day 8 and given the next week, the day of administration will be Day 15; Day 8 will be considered as missed. Once a dose of romidepsin or ixazomib is reduced, the dose may only be re-escalated after discussion with and approval by the sponsor investigator. If a delay occurs on day 1 of a cycle, then day 1 will be when the first dose of a cycle is given.

For a new cycle of treatment to begin or resumption of treatment within a cycle, the patient must meet the following criteria:

- ANC $\geq 1,000/\text{mm}^3$.
- Platelet count $\geq 75,000/\text{mm}^3$.
- Concurrent magnesium and potassium supplementation is allowed to maintain levels within a normal range.
- All other nonhematologic toxicity (except for alopecia) must have resolved to \leq Grade 1 or to the patient's baseline condition.

Hematologic toxicities:

Toxicity	Action
Within-Cycle (day 8 and 15) Dose Modifications 
 • If platelet count $< 30 \times 10^9/\text{L}$ or ANC $< 0.50 \times 10^9/\text{L}$ on treatment days 8 and 15 (for dose adjustments on day 1, see below). 	
 • Hold treatment • Obtain CBC with diff 2x/week until platelet count or ANC have reached goal outlined above • Upon recovery, reinitiate treatment at 1 dose level reduction as per section 6.3.
Dose Modifications for Subsequent Treatment Cycles 
 • ANC $< 1.0 \times 10^9/\text{L}$, platelet count $< 75 \times 10^9/\text{L}$ on day 1 of a cycle. 	
 • Hold romidepsin and ixazomib until resolution as per criteria above • Obtain CBC with diff 2x/week until platelet count or ANC have reached goal outlined above • Upon recovery, reinitiate treatment at 1 dose level reduction as per section 6.3. • The maximum delay before treatment may be discontinued is 21 days and at the discretion of the local PI.

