
 • Delay of > 2 weeks in the start of a subsequent cycle due inadequate recovery to goals outlined above. 	
 • Hold romidepsin and ixazomib until resolution as per criteria above • Obtain CBC with diff 2x/week until platelet count or ANC have reached goal outlined above

Toxicity	Action
	
 Upon recovery, reinitiate treatment at 1 dose level reduction as per section 6.3. The maximum delay before treatment may be discontinued is 21 days and at the discretion of the local PI.

 Grade 4 febrile neutropenia or thrombocytopenia 	
 Hold treatment Obtain CBC with diff 2x/week until platelet count or ANC have reached goal outlined above Upon recovery, reinitiate treatment at 1 dose level reduction as per section 6.3.

Non-Hematological Toxicity Dose Reductions Related to Study Drugs (except alopecia)

NCI CTCAE Grade	Romidepsin	Ixazomib
0-1	No change	No change
2-3	Hold until resolved to \leq Grade 1, then resume at same level	Hold until resolved to \leq Grade 1, then resume at same level with exceptions as outlined in table “Non-hematological Toxicity Dose Reductions specific to Ixazomib”
Second episode of grade 3 OR First episode 4 toxicity	Hold until resolved to \leq Grade 1, then resume at 1 dose level reduction as per section 6.3.	Hold until resolved to \leq Grade 1, then resume at 1 dose level reduction as per section 6.3.
Third episode of grade 3 OR Second episode 4 toxicity	Hold until resolved to \leq Grade 1, then resume at 1 dose level reduction as per section 6.3. If toxicity occurs at lowest dose level, then treatment should be discontinued	Hold until resolved to \leq Grade 1, then resume at 1 dose level reduction as per section 6.3 or discontinue based on local PI judgement If toxicity occurs at lowest dose level, then treatment should be discontinued

Non-hematological Toxicity Dose Reductions specific to Ixazomib:

Peripheral Neuropathy	

 New or worsening Grade 1 peripheral neuropathy with pain or Grade 2 	
 Hold study drug until resolution to Grade \leq 1 or baseline

 New or worsening Grade 2 peripheral neuropathy with pain or Grade 3 	
 Hold study drug until resolution to Grade \leq 1 or baseline Reduce study drug to next lower dose upon recovery

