7.2 On Treatment Evaluations

7.2.1 Cycle 1+, Day 1

- Laboratory assessments: CBC, CMP, Mg, LDH
 - **Note:** Cycle 1 Day 1 lab testing need not be repeated if completed within 7 days of starting protocol therapy.
- Correlative laboratory assessments: see section 7.2.3
- Office visit
- Physical Exam with vital signs and weight
- ECOG performance status
- Adverse event (AE) assessment

- Concomitant medication review
- Drug administration of romidepsin and ixazomib per dosing cohort

7.2.2 Cycle 1+, Day 8 and 15

- Laboratory assessment: CBC, CMP, Mg, LDH for first 3 cycles.
- Drug administration of romidepsin and ixazomib per dosing cohort

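### Section 6.2 orders a hold for painful Grade 1 neuropathy, but its release condition is already met at onset, so the written rule permits immediate ixazomib redosing

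*Combined protocol and SAP*

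**What the plan says.** Section 6.2 has a table of non-hematological dose rules specific to ixazomib, with three neuropathy rows.

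- Row 1 is triggered by "New or worsening Grade 1 peripheral neuropathy with pain or Grade 2". The action is "Hold study drug until resolution to Grade" 1 or lower, or baseline. There is no dose reduction.
- Row 2 is triggered by Grade 2 with pain, or by Grade 3. The release is the same, followed by a reduction to the next lower dose.
- Row 3 is Grade 4, which ends the drug.

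The general rule for restarting, which governs both drugs, is introduced by "For a new cycle of treatment to begin or resumption of treatment within a cycle, the patient must meet the following criteria". Its last item reads "All other nonhematologic toxicity (except for alopecia) must have resolved to" Grade 1 or lower, or the patient's baseline condition. In the general non-hematological table, Grade 0-1 calls for no change to either drug. That table points to the ixazomib-specific table only from its Grade 2-3 ixazomib cell.

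The scope is limited: "Dose modifications below are outlined for the Phase I portion of the trial". The Phase II rules are to be written once the MTD is known.

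**The concern.** A hold rule needs a release that is false when the trigger fires. Here the trigger depends on pain and the release depends only on grade, so a patient with new painful Grade 1 neuropathy satisfies both at once. One site may redose the same day and another may wait for the pain to settle, and both would be following the text.

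The stake is patient safety in Phase I. Section 10.1.6 lists peripheral neuropathy among the most common ixazomib adverse events. Section 1.3 puts it first among events leading to discontinuation of at least one regimen drug (45 patients). Neither figure is specific to painful Grade 1 events. The wording could also be copied into the Phase II rules.

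**Working it through.** The plan gives no figure to reproduce. The check is to enumerate the triggers and then search for a repairing rule.

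**Inputs.** The five neuropathy triggers and the release come from the ixazomib-specific table in Section 6.2. The table's rash row carries no hold and is not counted. Exclusion 13 in Section 3.2 bars neuropathy of Grade 2 or higher, so the entry grade *b* is 0 or 1.

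**Release test at onset.** With onset grade *g*, the release is met if *g* ≤ 1 or *g* ≤ *b*.

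| Trigger | Action | *g* | Met at onset, *b* = 0 | Met at onset, *b* = 1 |
|---|---|---|---|---|
| Grade 1 with pain | hold | 1 | yes | yes |
| Grade 2 | hold | 2 | no | no |
| Grade 2 with pain | hold, then reduce | 2 | no | no |
| Grade 3 | hold, then reduce | 3 | no | no |
| Grade 4 | discontinue | 4 | no release | no release |

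One of five triggers is released at onset. Either limb of the release is enough, so the baseline limb cannot rescue it. No minimum hold is stated.

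**Search for a pain condition elsewhere.**

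- The Section 6.2 restart criterion uses the same grade limit and does not mention pain.
- The general table leaves ixazomib unchanged at Grade 0-1.
- Section 5.5.1 allows observation for recovery, reductions or delays as the protocol indicates, and supportive treatment at the investigator's discretion. It sets no release.
- Section 6.4 lets the physician change therapy, and Section 13.1 provides weekly Phase I team meetings. Neither is a release rule.
- Section 5.6.2 points to Section 6 of the Investigator's Brochure for further management detail. That text cannot be checked here.

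**Likely intent.** Row 1 pairs Grade 1 with pain with Grade 2, and row 2 pairs Grade 2 with pain with Grade 3. Pain is treated as one grade higher, which suggests that a real hold was meant.

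**Test of a revised release.** Take the release as Grade 1 or lower without pain, or baseline in both grade and pain severity at entry, and apply it to a painful Grade 1 event.

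- Entry at Grade 0: pain is present and the grade is above entry, so the release is not met.
- Entry at painless Grade 1: pain is present and was absent at entry, so it is not met.
- Entry at painful Grade 1 with worse pain: severity is above entry, so it is not met. If baseline recorded pain only as present or absent, this patient would be released at onset again, so severity is needed.

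The count falls from 1 of 5 to 0 of 5.

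**Decision rules.** Under Section 6.1 a non-hematologic toxicity must be Grade 3 or 4 to be a DLT (Grade 5 of any kind also counts). Grade 1 neuropathy therefore does not enter the dose-finding model, and the CR thresholds do not refer to it.

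**The case against.** The strongest reply is that the row does order a hold and only the release is poorly worded. A clinician would read the row as meaning until the pain resolves, and the pattern of the table supports that. Sites also have investigator discretion, weekly meetings and possibly a fuller rule in the brochure. If the hold lapses at once, the patient is treated as the general table treats any Grade 0-1 event. No frequency is given and no statistical rule moves.

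Most of this stands, and it limits the size of the point. It does not remove it: the sensible reading has to be supplied by the reader, and the written criterion permits the opposite.

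A reader might infer more than the documents support:

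- That painful Grade 1 neuropathy requires no hold, or that the row is empty. A hold is ordered, and the same row works for Grade 2.
- That the neuropathy table fails as a whole. Four of the five triggers work.
- That sites have no other guidance. The brochure is cited but cannot be seen here, so this is unknown.
- That a number of lost doses or days measures the defect. Such figures would describe the effect of a corrected hold, and they depend on whether the cycle start is delayed.

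**Conclusion.** The point holds as a minor safety point about wording. For one of five neuropathy triggers, in the Phase I rules, the release is true when the hold begins, so immediate redosing complies with the text. This follows from the table alone, for either eligible entry grade.

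The clinical effect is unknown, because the documents do not say how often painful Grade 1 neuropathy occurs or what the brochure advises. That a longer hold was intended is an inference from the pattern of the table. The DLT definition, MTD selection and CR thresholds are unaffected.

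**What to change.** In the first neuropathy row, change the release to: Grade 1 or lower without pain, or the patient's baseline (grade and pain severity at entry). Grade 2 shares this cell, so the new wording governs its release too: a Grade 2 event that falls to Grade 1 but has become painful would stay held unless that matches the entry state.

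Row 2 may stay as it is. It could let a patient restart with painful Grade 1 neuropathy, but at a reduced dose. Leave the general restart criterion alone, because it also governs romidepsin. Add a pointer to the ixazomib-specific table in the general table's Grade 0-1 ixazomib cell, and carry the corrected wording into the Phase II rules.

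The change is one cell and one pointer in the next amendment. The running costs are small:

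- **Ixazomib doses are occasionally held or delayed.** Within a cycle a held dose is lost, since "Missed doses within a cycle will not be made up". If the whole cycle start waits, the doses move instead: "If a delay occurs on day 1 of a cycle, then day 1 will be when the first dose of a cycle is given".
- **Sites must ask about pain before the Day 8 and Day 15 doses.** Section 7.2.2 schedules only dosing and "Laboratory assessment: CBC, CMP, Mg, LDH for first 3 cycles" on those days; adverse events are assessed on Day 1.
- **Pain severity must be recorded at entry** for patients who enroll with Grade 1 neuropathy.
- **A long hold might raise the discretionary 21-day provision in Section 6.4.** That section does not say whether holding ixazomib alone counts as interrupting protocol therapy.

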6.3 Dose Levels for Dose Reductions for Phase I

Dose level	Romidepsin	Ixazomib
6	14 mg/m ² D 1, 8, 15	4mg D 1, 8, 15
5	14 mg/m ² D 1, 8	4mg D 1, 8, 15
4 (Starting dose)	10 mg/m ² D 1, 8, 15	4mg D 1, 8, 15
3	10 mg/m ² D 1, 8, 15	3mg D 1, 8, 15
2	10 mg/m ² D 1, 8, 15	3mg D 1, 8
1	10 mg/m ² D 1, 8, 15	2.3mg D 1, 8
0	Discontinue	Discontinue

6.4 Protocol Therapy Discontinuation

In addition to discontinuation from therapy related to toxicities as outlined in section 6.1, a subject will also be discontinued from protocol therapy and followed up per protocol under the circumstances outlined below. The reason for discontinuation of protocol therapy will be documented on the electronic case report form (eCRF).

- Documented disease progression
- The treating physician thinks a change of therapy would be in the best interest of the subject
- The subject requests to discontinue protocol therapy, whether due to unacceptable toxicity or for other reasons
 - If a subject decides to prematurely discontinue protocol therapy (“refuses treatment”), the subject should be asked if he or she may still be contacted for further scheduled study assessments. The outcome of that discussion should be documented in both the medical records and in the eCRF.
- A female subject becomes pregnant
- If protocol therapy is interrupted for ≥ 21 days and at the discretion of the local PI.

6.5 Protocol Discontinuation

If a subject decides to withdraw from the study (and not just from protocol therapy) all efforts should be made to complete the final study assessments. The site study team should contact the subject by telephone or through a clinic visit to determine the reason for the study withdrawal. If the reason for withdrawal is an adverse event, it will be recorded on the eCRF.

7. STUDY CALENDAR & EVALUATIONS

Cycle = 28 days	Screening	On Treatment Cycle 1+ 2			Every 3, 6 cycles	Safety follow up	Long-term Follow up ⁴
Days	-28 days ¹	1	8	15	1	30 days ^{2,3} post last dose	Every 3 months
Window		± 3	± 3	± 3	± 7	± 7	±15 days
REQUIRED ASSESSMENTS							
Informed Consent	X						
Review subject eligibility criteria	X						
Medical history, Demographics, Diagnosis & Staging	X						
Physical exam	X	X				X	
Vital signs ⁶ , height ⁶ , weight, ECOG Performance status	X	X				X	
EKG ⁷	X						
AEs & concomitant medications	X	X				X	
LABORATORY ASSESSMENTS							
Complete Blood Cell Count with diff, plts (CBC) ⁸	X	X	C1-3 ¹⁰	C1-3 ¹⁰		X	
Comprehensive Metabolic Profile (CMP) ⁹	X	X	C1-3 ¹⁰	C1-3 ¹⁰		X	
Mg, LDH	X	X	C1-3 ¹⁰	C1-3 ¹⁰		X	
HBV sAg, cAb; HCV Ab ¹¹ ; HIV screen ¹²	X						
Pregnancy test (serum or urine) WOCBP ¹³	-14d						
DISEASE ASSESSMENT ¹¹							
PET/CT Scan ¹⁴	X	pre C3, pre C5			X ¹⁴		[X] ⁴
Bone marrow biopsy ¹⁵	-60d	post C2 (if BM+, PET-)					
TREATMENT EXPOSURE							
Romidepsin ¹⁶		X	X	X ¹⁶			
Ixazomib ¹⁶		X	X	X ¹⁶			
CORRELATIVE STUDIES (SPECIMEN COLLECTION)							
Archival tissue or mandatory biopsy	X ⁵						
PBMC and plasma samples ¹⁸		pre-C1, C3, C5			X ¹⁸		
Whole Blood for somatic baseline ¹⁹		pre-C1					
BANKING SAMPLES (SPECIMEN COLLECTION) ²⁰							
Whole Blood		Pre-C1					
Serum and Plasma		Pre-C1, C3					
Unstained slides		Pre-C1					
FOLLOW-UP							
Survival status, Additional Cancer Therapy							X

Key to Footnotes

¹If screening (baseline) labs were performed within 7 days of D1 of treatment, these do not need to be repeated.

²A window of 3 days will be applied to all treatment study visits; for safety follow-up visit and tumor imaging, a 7-day window will apply.

³A safety follow-up visit will occur 30 days (± 7 days) after the last dose of treatment. AEs and SAEs will be collected for 30 days after discontinuation of the study drug. See Section 11.2.

⁴Subjects without documented disease progression will be followed for disease progression every 3 months for 2 years. Once disease progression is documented, subjects will enter a survival follow up period every 3 months for 1 year from the time of documented PD or for a total duration of 2 years after initiation of treatment, whichever is sooner.

⁵Archival tissue confirming disease relapse (after initial or any subsequent salvage therapy) is requested at screening. If archival tissue is unavailable or insufficient, a biopsy is mandatory. FFPE for IHC testing, RNA-Seq, WES, and HTS must be available. Verification of sufficient tissue is required prior to C1D1. Biopsy samples will include FFPE and snap frozen tissue for analysis. See CLM for collection, processing, labeling and shipping instructions.

⁶Vital signs to include temperature, blood pressure, heart rate, respiratory rate. Height at screening only.

⁷EKGs will also be obtained if Zofran or other 5-HT₃ serotonin receptor antagonists are used as anti-emetics. In this instance, EKGs should be performed at least 2 weeks after initiation of the medication to assess the QT interval

⁸CBC to include white blood cell count, hemoglobin, hematocrit, platelets, differential

⁹CMP to include sodium, potassium, chloride, creatinine, blood urea nitrogen, glucose, AST, ALT, total bilirubin, alkaline phosphatase, total protein, albumin, magnesium and lactate dehydrogenase (LDH).

¹⁰Laboratory assessments for cycles 1-3.

¹¹Perform if abnormal transaminases are present

¹²Perform if patient has risk factors for HIV

¹³For women of childbearing potential (WOCBP): urine or serum β hCG, within 14 days prior to study registration. If a urine test is positive or cannot be confirmed as negative, a serum pregnancy test will be required.

¹⁴Tumor imaging to continue pre-Cycle 3 and 5 and then every 3 cycles thereafter until 24 months after initiation of study treatment, and then every 6 cycles, or until disease progression or at time of suspected clinical progression.

¹⁵Must be performed within 60 days of C1D1. If the bone marrow is positive and the PET is negative for bone marrow uptake, then a confirmatory bone marrow biopsy will be repeated at the time of first radiographic CR. If the bone marrow is positive and the PET is positive for bone marrow uptake, then a bone marrow biopsy is not required at the time of first CR.

¹⁶Romidepsin and ixazomib administration per dosing cohort from Phase I. Ixazomib is not given on Day 15 for dose levels 1 and 2. Romidepsin is not given on Day 15 for dose level 5. See 6.3.

¹⁷[removed]

¹⁸PBMC and plasma for future MRD assessments at Pre-Treatment C1D1, C3D1, C5D1, and at every timepoint for response assessment.

¹⁹Whole blood is to be collected at Pre-Treatment C1D1 for somatic baseline.

²⁰Whole blood and unstained slides, if available, will be collected prior to treatment on Cycle 1 Day 1. Serum and plasma will be collected prior to treatment on C1D1 and C3D1.

7.1 Screening Evaluations

7.1.1 Within 28 days prior to registration for protocol therapy

- Informed Consent
- Review Subject eligibility criteria
- Medical history
 - Complete medical and surgical history, history of infections, social history, smoking, alcohol and illicit drug use history
- Demographics
 - Age, gender, race, ethnicity, trial awareness question
- Staging (See appendix II)
- Diagnostic pathology specimen
 - From a recently obtained (within 6 months) lymph node biopsy confirming relapsed or refractory disease or
 - Lymph node biopsy (core-needle or excisional) at enrollment in patients without sufficient archived diagnostic tissue
- Office visit with physical exam
- Height, weight
- Vital signs
 - Temperature, blood pressure, heart rate, respiratory rate
- ECOG performance status (See appendix I)
- EKG, 12-lead
- Adverse event (AE) assessment
 - Baseline AEs will be assessed, see section 11 for AE monitoring and reporting
- Concomitant medication review
- Laboratory assessments
 - CBC, CMP, Mg, LDH
 - HBV sAg and cAb, HCV Ab if abnormal transaminases
 - HIV screen if risk factors present
 - (within 14 days) Pregnancy test (urine or serum) for WOCBP
- PET/CT scan
- Diagnostic specimen (FFPE) for correlative studies

7.2 On Treatment Evaluations

7.2.1 Cycle 1+, Day 1

- Laboratory assessments: CBC, CMP, Mg, LDH
 - **Note:** Cycle 1 Day 1 lab testing need not be repeated if completed within 7 days of starting protocol therapy.
- Correlative laboratory assessments: see section 7.2.3
- Office visit
- Physical Exam with vital signs and weight
- ECOG performance status
- Adverse event (AE) assessment

- Concomitant medication review
- Drug administration of romidepsin and ixazomib per dosing cohort

7.2.2 Cycle 1+, Day 8 and 15

- Laboratory assessment: CBC, CMP, Mg, LDH for first 3 cycles.
- Drug administration of romidepsin and ixazomib per dosing cohort

7.2.3 Correlative laboratory assessments

- PBMC and plasma for future MRD assessments on C1D1, C3D1, C5D1, and at every time point for response assessment.
- Whole blood is to be collected at Pre-Treatment C1D1 for somatic baseline.
- Archival FFPE or diagnostic biopsy frozen sections for future RNA-Seq, WES, and HTS.
- Archival FFPE or diagnostic biopsy slides for IHC (TNFR2 and HR23B)

7.2.4 Banking Sample Collection

- Whole blood, serum and plasma will be collected prior to treatment on Cycle 1 Day 1
- Serum and plasma will be collected prior to treatment on Cycle 3 Day 1
- Unstained slides will be requested from the subject's pre-treatment tumor sample, if available.

7.2.5 Disease assessment

- PET/CT scan pre-cycle 3 and 5, and then every 3 cycles thereafter until 24 months after initiation of study treatment, and then every 6 cycles, or until disease progression or at time of suspected clinical progression of disease.
- Bone marrow biopsy. If the baseline bone marrow is positive and the PET is negative for bone marrow uptake, then a bone marrow biopsy will be repeated after cycle 2. If the bone marrow is positive and the PET is positive for bone marrow uptake, then a bone marrow biopsy will not be repeated.

7.3 Safety Follow-up Evaluations

A safety follow-up visit should occur when subjects permanently stop study treatment for whatever reason (toxicity, progression, or at discretion of site investigator) and should be performed 30 days (± 7 days) after the last dose of treatment. Subjects who have an ongoing \geq grade 2 or serious AE (SAE) at this visit will continue to be followed until the AE resolves to \leq Grade 1 or baseline, is deemed clinically insignificant, and/or until a new anti-cancer treatment starts, whichever is earlier.

- Office visit
- Laboratory assessment: CBC, CMP, Mg
- Physical Exam with vital signs and weight
- ECOG performance status
- Adverse event (AE) assessment
- Concomitant medication review

7.4 Long Term Follow-up Evaluations

All subjects will be followed until documented disease progression. Subjects who discontinue treatment for any reason without documented disease progression will be followed for disease progression every 3 months for 2 years.

Once disease progression is documented, subjects will enter a survival follow up period every 3 months for 1 year from the time of documented progression or for a total duration of 2 years after initiation of treatment, whichever is sooner. Follow up may be accomplished via clinic visit, phone call, or other avenues as appropriate.

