
(including vorinostat, romidepsin, and belinostat) abolishes GATA-3 DNA binding in both TCL cell lines and primary samples and the expression of its gene targets. We have not observed any alteration in total GATA-3 expression or nuclear localization following HDACi treatment. In coupled immunoprecipitation and immunoblotting studies, we have demonstrated that HDAC inhibition regulates the extent of GATA-3 acetylation (data not shown). These innovative findings suggest that HDAC inhibition disrupts GATA-3 DNA binding and target gene expression. If so, this finding would have significant clinical implications, suggesting that HDAC inhibitors may overcome chemotherapy resistance in GATA-3-expressing T-cell lymphomas.

GATA-3 expression is not only NF- κ B dependent^{38,57}, but is also required for the homeostatic survival^{57,58}, differentiation⁵⁹, and migration⁶⁰ of conventional T-cell subsets. Consistent with its role in conventional T cells, we have previously shown that GATA-3 is an NF- κ B target gene in malignant T cells and confers their resistance to chemotherapy in a cell-autonomous manner³⁸. Not surprisingly, GATA-3 expression has both diagnostic and therapeutic implications⁴⁰, and its expression has successfully identified high-risk PTCL patients who are unlikely to achieve a remission with conventional chemotherapeutic agents⁴⁴. Therefore, the observation that ixazomib led to significant inhibition of both NF- κ B and GATA-3 in primary TCL specimens *ex vivo* and following one month of treatment in the single responder treated in this study is noteworthy. Consistent with our findings, Ravi et. al. observed that ixazomib induced apoptosis in multiple T-cell lymphoma cell lines and was associated with widespread changes in gene expression.

Proteasome inhibition is synergistic with other therapeutic strategies, including HDAC inhibition⁶¹, and likely overcomes mechanisms of chemotherapy resistance in T-cell lymphomas^{22,36}. While the median OS in rel/refr PTCL is <6 months^{7,62,63}, a subset of patients treated with romidepsin achieve a durable CR (>12 months), that is associated with prolonged OS¹².

Therefore, we propose a multi-center phase II study with ixazomib and romidepsin in patients with relapsed/refractory PTCL. Since this is a novel combination, the phase I endpoint is to determine the dose limiting toxicity and maximum tolerated dose and the phase II endpoint is to determine the CR rate of this combination.

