2.2.2 Secondary Endpoints

- OR, defined as complete or partial metabolic response recorded from first day of treatment until disease progression/recurrence or initiation of new antineoplastic therapy, as per the Lugano response criteria.
- DOR, defined as time that measurement criteria are met for complete or partial metabolic response (whichever status is recorded first) until disease progression/recurrence or initiation of new antineoplastic therapy, as per the Lugano response criteria.
- TTNT defined as the date of initiation of treatment until death or the date of initiation of the next treatment.
- OS, defined as time from first day of treatment to time of death.

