12.7.2 Analysis Plans for Secondary Objectives

ORR at one year will be summarized for the Efficacy population, including appropriate uncertainty. DOR in the Efficacy population will be summarized via Kaplan-Meier (KM) methods and confidence intervals, with time = 0 defined as the date of first response. TTNT and OS will also be summarized with KM methods, with time = 0 defined as the date of first dose of cycle 1.

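### Survival follow-up stops one year after progression, so OS censoring depends on progression date and the Kaplan-Meier curve is unreliable from about month 14

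*Combined protocol and SAP*

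**What the plan says.** Section 2.2.2 gives the endpoint: "OS, defined as time from first day of treatment to time of death". Section 12.7.2 gives the analysis: "TTNT and OS will also be summarized with KM methods", with time zero at the first dose. It states no censoring rule and no sensitivity analysis.

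Follow-up is set in section 7.4. Before progression: "All subjects will be followed until documented disease progression". Patients who stop treatment without progression "will be followed for disease progression every 3 months for 2 years"; the start of those 2 years is not stated. After progression, survival is followed "for 1 year from the time of documented progression or for a total duration of 2 years after initiation of treatment, whichever is sooner". Footnote 4 of the study calendar has the same rule: "subjects will enter a survival follow up period every 3 months for 1 year from the time of documented PD", with the same 2-year cap.

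Section 7.2.5 schedules "PET/CT scan pre-cycle 3 and 5, and then every 3 cycles thereafter until 24 months after initiation of study treatment", and less often after that, so progression after month 24 can still be found.

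**The concern.** Kaplan-Meier treats a patient censored at a given time as having the same future risk of death as those still under observation. Here the censoring time follows from the progression date. Patients who progress early and are alive a year later leave the risk set, while those who progressed later or not at all remain. Section 1.4 gives reason to think that these groups differ: it says that "median OS in rel/refr PTCL is <6 months" and links durable complete response to longer survival.

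At stake is the late part of the OS curve, the part a reader would consult for durable benefit. Section 12.7.3 also lists OS among the outcomes to be related to biomarker expression, so that analysis would use the same data.

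**Working it through.** **1. The plan's own figure.** The documents give no OS estimate, event count or precision. The one relevant figure is the study duration in section 12.3: 48 patients / 2 per month = 24 months, plus 12 months for the last patient = 36 months. This matches the stated 3 years.

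**2. The follow-up rule.** For progression at month p, survival follow-up ends at min(p + 12, 24).

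| Progression | Survival follow-up ends |
|---|---|
| month 2 | min(14, 24) = 14 |
| month 6 | min(18, 24) = 18 |
| month 12 | min(24, 24) = 24 |
| after month 24 | limit already passed: none |
| none | at progression, or after 2 years if off treatment |

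**3. Onset.** The first scheduled scan is before cycle 3: 2 × 28 = 56 days, about month 2. Censoring by this rule therefore starts at about 2 + 12 = month 14. Earlier clinical progression could bring it forward, but never before month 12.

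**4. Size.** The documents give no progression-free or post-progression survival, so these inputs are assumptions:
- 15% of patients have a median PFS of 36 months and the rest 3 months.
- 10% of PFS events are deaths.
- Post-progression survival (PPS) has a constant hazard, with median 3 to 9 months.

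The simulation used 400,000 patients per setting. Bias = Kaplan-Meier minus true survival. The approximate standard error (SE) is √[S(1 − S)/30], with 30 the maximum Efficacy population in section 12.4; for example √(0.202 × 0.798/30) = 7.3 points. Section 12.7.2 does not say which population is used for OS, so n = 30 is also an assumption.

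| Median PPS (months) | Median OS (months) | True 24-month OS | Kaplan-Meier | Bias (points) | SE (points) | Censored alive early |
|---|---|---|---|---|---|---|
| 3 | 7.9 | 12.2% | 14.3% | +2.1 | 6.0 | 5% |
| 4 | 9.1 | 14.4% | 17.9% | +3.5 | 6.4 | 9% |
| 6 | 11.3 | 20.2% | 25.5% | +5.3 | 7.3 | 19% |
| 9 | 14.5 | 29.6% | 35.7% | +6.1 | 8.3 | 30% |

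In the same settings the bias is 0 at month 12, +0.4 to +0.7 points at month 15 and +1.0 to +2.1 at month 18.

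**5. Nearer the historical median.** This second model assumes median PFS 2 months, median PPS 3 months and a death rate without progression of 0.005 per month. With no durable responders, median OS is 5.9 months and the 24-month bias is +0.2 points. With 10% who never progress, median OS is 6.5 months and Kaplan-Meier gives 13.0% against 9.8% true: +3.2 points, SE 5.4.

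**6. Direction.** Assume median PFS 4 months, 15% who never progress, and median PPS 4 months for progressors who are not long-term survivors. If 20% of progressors survive long term, the 24-month bias is about −0.1 points. If 30% do, it is −1.3 to −1.4.

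**7. After month 24.** Assume median PFS 4 months, median PPS 6 months and 15% who never progress. At month 30, true OS is 19.5% and the planned curve shows 30.3%, about 11 points too high.

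**8. Common cut-off.** In the model of step 7, 24-month OS is 26.1% true, 31.5% under the plan and 26.1% if everyone is followed to month 24.

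**The case against.** The strongest reply is that little hangs on this. OS is secondary and descriptive, with no test, no 18- or 24-month landmark and no specified comparison. The documents' OS benchmark for relapsed or refractory disease is a median below 6 months, and a median below 12 months cannot be touched by this rule. The bias in step 4 is less than one SE. All of this stands, and it limits the point to a cheap improvement.

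A reader might go further in three ways that the documents do not support.

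- **That the curve is certainly too high.** Upward is the expected direction given section 1.4, but it depends on how long progressors live, which the documents do not say. Step 6 shows the bias vanishing or slightly reversing.
- **That no analysis could remove the bias.** In the model of step 4, an Aalen-Johansen illness-death estimator applied to the censored data recovers the truth. True / Kaplan-Meier / Aalen-Johansen at 24 months are 12.2/14.3/12.3, 14.5/17.9/14.5, 20.3/25.7/20.3 and 29.7/35.9/29.9% (a separate run, hence small differences from the table). It works because that model makes the hazard after progression independent of time since progression. The trial cannot test this beyond 12 months after progression, because survival follow-up ends there.
- **That every patient without progression is observed to month 24.** Section 12.3 allows the last patient only up to 1 year. That cut-off depends on entry date, not prognosis, so it costs precision without causing this bias. With added administrative censoring spread evenly over months 12 to 36, the 24-month bias in the step 7 model was still +5.3 points.

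**Conclusion.** The concern holds in a limited form. Section 7.4 and footnote 4 make OS censoring depend on progression date, so plain Kaplan-Meier violates independent censoring from about month 14. Estimates up to month 12 are sound. Under the assumed inputs of step 4, the expected error is about +1 to +2 points at month 18 and +2 to +6 at month 24, below one SE at n = 30. It is nonetheless systematic and avoidable.

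The gap after month 24 does not depend on those inputs. Deaths of patients who progress after that point are not collected, so a curve drawn further misses them; only the size in step 7 is assumed. The CR endpoint, the interim futility rule and the final CR decision do not use these data.

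**What to change.** In section 7.4 and calendar footnote 4, follow every treated patient for survival every 3 months until death, withdrawal or a common cut-off measured from first dose (24 months or study closure), whatever the progression date. Delete the limit of one year from progression. In section 12.7.2, state that the OS curve is not drawn beyond the common cut-off.

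The cost is protocol wording and a few extra quarterly contacts per surviving progressor; section 7.4 already allows these by phone.

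If follow-up is not extended, either end the OS curve at 12 months or pre-specify a progression-based sensitivity analysis: inverse-probability-of-censoring weighting or a multistate estimator. The plan should then say that this analysis assumes that the hazard of death does not depend on time since progression.
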